September 1, 2014

Study Title: Measurement of Cerebral Blood Flow Using Transcranial Doppler Ultrasound in Children with Sickle Cell Disease NCT: NCT02090881 Protocol ID: 13HH0858

Patients with SCD age 2 to 16 years attending our tertiary paediatric haematology clinic for stroke surveillance were eligible. The study was conducted as part of a higher degree in vascular imaging and hence the study duration was limited to six months. Based on patient numbers within the service, we aimed to study 25 consecutive patients referred to the vascular sciences department for routine TCD scanning. Ethical approval was obtained from the local research ethics committee (ref 13/LO/1503) and IRAS ID 133045) and written informed consent was obtained from legal guardians. A pulsatile flow simulating phantom was used to eliminate patient variability. Study participants were scanned by a single operator with imaging TCCD. Initially a full TCD assessment was performed using the non-portable Philips IU-22 with a S5-1 phased array transducer (5.0-1.0MHz). The measurement was then repeated in every patient in only the MCA on each side of the head using the portable Zonare Z-One scanner with a P4-1C phased array transducer (4.0-1.8MHz). For both examinations, a standardised screening protocol was used recording velocities from the transtemporal windows, a 5mm sample volume size, with no angle correction. Gain was adjusted in order to clearly see the spectral Doppler velocity waveform without the presence of noise in the background. For the purpose of this study, the TAMM velocities were compared because stroke risk categorisation according to the STOP trial was based on TAMM velocity, not peak systolic or end diastolic velocities. Each study was categorised as normal, conditional, abnormal or inadequate according to criteria previously developed by the STOP protocol. The participants were not permitted to sleep during the scan to avoid increase in blood carbon dioxide levels in sleep, which can result in increase in TCD velocities. Methods Patients with SCD age 2 to 16 years attending our tertiary paediatric haematology clinic for stroke surveillance were eligible. The study was conducted as part of a higher degree in vascular imaging and hence the study duration was limited to six months. Based on patient numbers within the service, we aimed to study 25 consecutive patients referred to the vascular sciences department for routine TCD scanning. Ethical approval was obtained from the local research ethics committee (ref 13/LO/1503) and IRAS ID 133045) and written informed consent was obtained from legal guardians.

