
A pulsatile flow simulating phantom was used to eliminate patient variability. Study participants were scanned by a single operator with imaging TCCD. Initially a full TCD assessment was performed using the non-portable Philips IU-22 with a S5-1 phased array transducer (5.0-1.0MHz). The measurement was then repeated in every patient in only the MCA on each side of the head using the portable Zonare Z-One scanner with a P4-1C phased array transducer (4.0-1.8MHz). For both examinations, a standardised screening protocol was used recording velocities from the transtemporal windows, a 5mm sample volume size, with no angle correction. Gain was adjusted in order to clearly see the spectral Doppler velocity waveform without the presence of noise in the background. For the purpose of this study, the TAMM velocities were compared because stroke risk categorisation according to the STOP trial was based on TAMM velocity, not peak systolic or end diastolic velocities. Each study was categorised as normal, conditional, abnormal or inadequate according to criteria previously developed by the STOP protocol. The participants were not permitted to sleep during the scan to avoid increase in blood carbon dioxide levels in sleep, which can result in increase in TCD velocities.

Study Title: Measurement of Cerebral Blood Flow Using Transcranial Doppler Ultrasound in Children with Sickle Cell Disease NCT: NCT02090881 Protocol ID: 13HH0858 Statistical Analysis Spearman's Correlation Coefficients were calculated to assess the relationships between different parameters in

September 1, 2014

order to assess the strength of the association between the two measures. Intra-class Coefficient Correlation (ICC) and 95% confidence intervals were used to provide a measure of the strength of the association between the measurements from both pieces of equipment and therefore the validity of the measurement. It has been stated that $ICC > 0.75$ implies acceptable validity.

BlandAltman plots were used to estimate the agreement between TAMM velocity measurements by determining how much the velocity from one machine differs from another. Statistical analyses were performed using SPSS Statistics version 21 (IBM). The level of statistical significance was defined as $p < 0.05$.

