Conclusion The purpose of this pilot study was to evaluate the use of a portable ultrasound machine by comparison with an established laboratory-based ultrasound machine. This study demonstrated complete agreement in stroke risk categorisation between the two instruments. As a pilot study, it confirms the feasibility and clinical significance of this investigation. A larger sample size with a greater range in TAMM velocities is needed to further investigate the correlation between different ultrasound machines at extremes of measurement such as very high or very low velocities. Further evidence is needed in order to establish the implications these differences may have on screening

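### The plan does not estimate whether the difference between machines depends on velocity, although stroke-risk category is decided on velocity

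*Combined protocol and SAP*

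**What the plan says.** The Methods section explains the choice of endpoint: "stroke risk categorisation according to the STOP trial was based on TAMM velocity". Each child has a full examination on the laboratory machine. The reading is then repeated "in only the MCA on each side of the head using the portable Zonare Z-One scanner", which gives up to two pairs per child. The sample size comes from feasibility: "Based on patient numbers within the service, we aimed to study 25 consecutive patients".

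The Statistical Analysis section names three tools. Spearman correlation and the ICC describe strength of association, with this yardstick for the ICC: "It has been stated that $ICC > 0.75$ implies acceptable validity". For agreement, "BlandAltman plots were used to estimate the agreement between TAMM velocity measurements", and the sentence ends "by determining how much the velocity from one machine differs from another". It mentions no check for a trend with velocity, no log or ratio scale, no acceptable difference and no estimate at a STOP cut-point. The significance rule is general: "The level of statistical significance was defined as $p < 0.05".

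Separately, each examination is assigned a STOP category, and the Conclusion reports that the two machines never disagreed on category. The Conclusion also asks for a larger sample with a wider velocity range to study the machines "at extremes of measurement such as very high or very low velocities".

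**The concern.** The clinical use of the portable machine is to place a child on one side or the other of a velocity cut-point. The useful question is therefore how far the machines differ near the cut-points, not only how far they differ on average. If the difference rises or falls with velocity, an average over all children does not describe it where the decision is made.

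The other planned summaries do not answer this. A difference proportional to velocity leaves rank order intact, so Spearman is almost unaffected. The ICC is driven mainly by the spread between children and can pass 0.75 comfortably. Category agreement bears directly on the decision, but a machine that misreads near a cut-point is exposed only by readings near that cut-point, and the documents do not say how many there were. A reader could take three favourable summaries as evidence of agreement at the cut-points when none of them estimates it.

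**Working it through.** **No plan figure to reproduce.** The only design figure is 25 patients, taken from service numbers. No SD, margin, limits of agreement or velocity distribution is given. What follows is an illustration.

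**Inputs from the documents.** n = 25 children; up to 2 × 25 = 50 pairs; significance level 0.05 (taken as two-sided); ICC threshold 0.75.

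**Assumed inputs.** Difference d = a + b(v − mean v) + e, where v is the mean of the two readings. Slope b is 0.05 to 0.20, SD of v (SDv) is 20 to 40 cm/s, and residual SD (SDe) is 8 to 16 cm/s. The central case is b = 0.10, SDv = 30, SDe = 12. The sign of b does not affect the sizes below.

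**1. What a single average difference leaves out.** At a distance D from the mean velocity it is b × D. At D = 40 cm/s this is 2, 4 and 8 cm/s for b = 0.05, 0.10 and 0.20. At D = 80 cm/s it is 4, 8 and 16 cm/s.

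**2. Whether the ICC would show it.** With zero average difference, ICC = (SDv² − Vd/4) / (SDv² + Vd/4), where Vd = SDe² + b²SDv². In the central case Vd = 144 + 9 = 153, so ICC = (900 − 38.25)/(900 + 38.25) = 0.92. A stronger trend (b = 0.20, SDv = 25) gives Vd = 89 and ICC 0.93 for SDe = 8, and Vd = 169 and ICC 0.87 for SDe = 12. All pass 0.75.

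**3. Effect on limits of agreement, if one constant pair were reported.** The half-width is 1.96 × √Vd. In the central case this is 1.96 × √153 = 24.2 cm/s. At 2 SD above the mean velocity the true centre has moved by 0.10 × 60 = 6.0 cm/s and the true upper limit is 6.0 + 1.96 × 12 = 29.5 cm/s. There, 7.0% of differences fall outside the constant limits instead of 5%. Across the grid the share is 5.1% to 22.0%.

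**4. What 25 children can show.** The slope test uses a noncentral t with ncp = b × SDv × √(n − 1)/SDe and n − 2 df.

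| Slope | Power, n = 25 | Power, 50 pairs taken as independent |
|---|---|---|
| 0.05 | 0.06 to 0.22 | 0.07 to 0.40 |
| 0.10 | 0.09 to 0.65 | 0.14 to 0.93 |
| 0.20 | 0.22 to about 1.00 | 0.40 to about 1.00 |

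The central case gives 0.22 and 0.40. The last column is optimistic, because the two sides of one child are correlated.

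**5. Precision of the estimates at n = 25 (t = 2.07, central case).** The 95% half-width of the slope is 2.07 × 12/(30 × √24) = 0.17. The half-width of the predicted difference at 2 SD above the mean velocity is 2.07 × 12 × √(1/25 + 4/24) = 11.3 cm/s. At 3 SD it is 2.07 × 12 × √(1/25 + 9/24) = 16.0 cm/s (10.7 if SDe = 8).

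**6. Precision of a constant limit.** The 95% half-width of one limit is t × √(1/n + 1.96²/(2(n − 1))) = 0.72 SD of the differences at n = 25, and 0.49 SD at 50 independent pairs. In the central case 0.72 × √153 is about 8.9 cm/s, larger than the 6.0 cm/s shift.

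**The case against.** Four points on the other side have force.

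- **The plot itself shows a trend.** A Bland-Altman plot conventionally sets the difference against the mean, so a dependence on velocity can be seen. This stands. But no rule for reading the plot is given, and inspection yields no estimate or interval at a cut-point.
- **The category comparison addresses the cut-points.** It does, and no discordance was reported. Its weight depends on how many readings lay close to a cut-point, which is not stated.
- **The limitation is disclosed.** The Conclusion calls the study a pilot and asks for a wider velocity range. This stands for velocities outside the range observed. Within that range the existing pairs permit an estimate.
- **The sample is too small for a useful test.** This also stands, as the power figures show. It argues against relying on a p-value, and not against reporting the slope with its interval.

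A reader might go further and infer that the plan pools all velocities into one constant-bias pair of limits, so that a growing difference is averaged away and missed. The documents do not support that: the text names plots, and mentions neither limits nor a constant-bias model. Nor do they give evidence that the difference grows with velocity, or that routine patients mostly lie away from the cut-points.

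Dramatic figures can also be produced at the far end of an assumed distribution. With SDv = 25 and a slope of −0.2, the difference 75 cm/s above the mean velocity is −15 cm/s, and 33% (SDe = 8) or 19% (SDe = 12) of differences there fall below a constant lower limit. But 75 cm/s is 3 SD. About 0.13% of readings would exceed it, or 0.07 expected among 50, so that point would almost always lie outside the data.

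**Conclusion.** The point holds as an omission: dependence of the difference on velocity is not estimated, and the other planned summaries cannot stand in for that estimate. It does not show that the analysis performed was wrong, that a trend exists, or that the category result is false.

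The size is unknown. Under the assumed ranges, an average difference would misstate the difference at 40 to 80 cm/s above the mean velocity by 2 to 16 cm/s. In the central case the shift at 2 SD is smaller than the sampling error of a limit of agreement. All of this rests on assumed slopes and SDs and on a linear trend with constant residual spread. With about 25 children a non-significant slope does not rule out a trend, so any conclusion should rest on the interval. The change is worth making, and is proportionate for a pilot.

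**What to change.** Add to the Statistical Analysis section:

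1. Regress the difference (portable minus standard) on the mean of the two readings, with child as the cluster because both MCAs are measured. Report the slope with its 95% CI, and do not treat a non-significant p-value as evidence of no trend.
2. Report the predicted difference and limits of agreement, each with a CI, at every STOP cut-point inside the observed velocity range. Use a log or ratio scale if spread grows with velocity.
3. For any cut-point outside that range, state that agreement there was not assessed.
4. Beside the category result, give the number of readings near each cut-point, with nearness defined.

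The cost is one extra regression on data already held and a few sentences of reporting. The intervals near the cut-points will be wider than those for an overall average. That is the downside, and it shows honestly what a pilot of this size can say.

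### The Conclusion says complete STOP category agreement was demonstrated, but no named analysis measures category discordance; zero in the target 25 children would leave up to 13.7% possible (exact two-sided 95% limit)

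*Combined protocol and SAP*

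**What the plan says.** Methods give the reason for comparing mean velocities: "TAMM velocities were compared because stroke risk categorisation according to the STOP trial was based on TAMM velocity". They then describe a categorical result: "Each study was categorised as normal, conditional, abnormal or inadequate according to criteria previously developed by the STOP protocol".

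The first machine was used for a full TCD assessment. For the portable machine, "The measurement was then repeated in every patient in only the MCA on each side of the head". The sample size was a feasibility target: "we aimed to study 25 consecutive patients referred to the vascular sciences department for routine TCD scanning".

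Statistical Analysis names three tools:
- Spearman correlation.
- The ICC with a 95% confidence interval, with the remark "It has been stated that $ICC > 0.75$ implies acceptable validity".
- Bland-Altman: "BlandAltman plots were used to estimate the agreement between TAMM velocity measurements".

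It names no cross-table, percent agreement, kappa or interval for the categories.

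The Conclusion states: "This study demonstrated complete agreement in stroke risk categorisation between the two instruments". It also calls the study a pilot and says: "A larger sample size with a greater range in TAMM velocities is needed to further investigate the correlation between different ultrasound machines". It closes by saying that more evidence is needed on what the differences might mean for screening.

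**The concern.** The Conclusion's statement about how the machines compare concerns the STOP category, but the analysis section describes nothing that estimates category agreement. Because category is based on TAMM velocity, the three listed analyses bear on the question, but only indirectly. A correlation, an ICC or limits of agreement in velocity do not say how often the two machines put the same child in different categories, or how precisely that frequency is known.

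The word demonstrated, with no count or interval attached, can be taken as a property of the two instruments. In a sample of about 25, seeing no discordance is compatible with a true rate well above zero. Category is the result that stroke surveillance uses, so a reader considering the portable machine would want to know how much disagreement remains possible.

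**Working it through.** **Inputs**
- Number of children: 25, the target in Methods. The supplied text does not give the number analysed, so 20 to 30 is shown as an assumed range.
- Discordant children: 0, from the Conclusion's statement of complete agreement.
- Confidence level: 95%, the level the plan uses for the ICC. Two-sided is assumed, because the plan does not state sidedness.
- Unit: one classification per child per machine.

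**The plan's own figure.** There is nothing to reproduce. The 25 comes from service numbers and a six-month limit, with no power or precision calculation behind it, and no interval for category agreement is given in the supplied text.

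**Formula.** With 0 discordances in n children, the exact (Clopper-Pearson) two-sided 95% upper limit U for the true discordance solves (1 − U)^n = 0.025, so

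U = 1 − 0.025^(1/n).

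**Results**

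| n | Upper limit for discordance | Lower limit for agreement |
|---|---|---|
| 20 (assumed) | 1 − 0.025^(1/20) = 16.8% | 83.2% |
| 25 (target) | 1 − 0.025^(1/25) = 13.7% | 86.3% |
| 30 (assumed) | 1 − 0.025^(1/30) = 11.6% | 88.4% |

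**Cross-check.** The chance of seeing 0 of 25 discordant when the true rate is q is (1 − q)^25:
- q = 5%: 0.95^25 = 27.7%
- q = 10%: 0.90^25 = 7.2%
- q = 13.7%: 0.863^25 = 2.5%

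So a machine pair that disagreed in 1 child in 20 would still show complete agreement in more than a quarter of studies of this size.

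**Sensitivity to the choice of limit at n = 25.** A one-sided 95% limit is 1 − 0.05^(1/25) = 11.3%, and the Wilson two-sided limit is 13.3%. The conclusion does not depend on the choice. Counting 50 sides of the head as independent would give 1 − 0.025^(1/50) = 7.1%, but that ignores the correlation between the two sides of one child.

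**How many children a tighter limit needs.** Zero discordances bring the limit to 5% or less only from n = ln(0.025)/ln(0.95), rounded up to 72.

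**The case against.** The strongest reply is that the Conclusion already limits itself. It labels the study a pilot, asks for more patients and a wider velocity range, and ends by saying that the meaning of machine differences for screening still has to be established. This stands, and it is the main reason the point is minor. Even so, the larger-sample sentence is about correlation at extreme velocities, the closing sentence gives no figure, and neither tells a reader how much category discordance the data leave open.

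Second, the sentence can be read as a plain description of this sample. That is a fair reading, and on it the complaint is mostly about wording. Giving x of n with an interval would remove the ambiguity.

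Third, counts or an interval may exist in a results report. The supplied text has no Results section, so a reader might infer that no category table or bound was ever produced. The documents do not support that inference.

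Two other stronger readings should be resisted. A reader might infer that the ICC criterion of 0.75 lets through a particular rate of misclassification. Any such figure would need a velocity distribution and category frequencies that the documents do not give. A reader might also infer that the unit of categorisation and the place of inadequate scans are undefined. Methods say that each study was categorised and list inadequate among the four categories, so the natural reading largely settles both. Likewise, comparing MCA with MCA is the natural reading of the design; a table need only say so.

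**Conclusion.** The point holds as a minor reporting matter. No named analysis yields a category discordance rate or its uncertainty, and the Conclusion's statement on categories is firmer than about 25 children can support. On the target of 25, with one classification per child and no discordances, true discordance of up to 13.7% is not excluded (exact two-sided 95% limit). The corresponding figures are 16.8% at 20 children and 11.6% at 30. These limits are conditional on an analysed number that the supplied text does not give.

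This is not evidence that the machines disagree, and it does not show that any named analysis is wrong. Nor does it invalidate the study as a pilot.

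**What to change.** Add a cross-table of STOP category by machine, labelled post hoc, with one classification per child. Base both categories on the MCA velocities that both machines measured, and show the conditional, abnormal and inadequate counts. Report percent agreement with an exact (Clopper-Pearson) 95% confidence interval.

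Reword the Conclusion to say that *categories agreed in x of n children (95% CI …)*. Add that agreement among conditional or abnormal children is not established unless the counts support it. Keep the existing caveats.

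The cost is one table and one reworded passage, from data already collected, with no new patients and no change to design. The downside is a less favourable headline.

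### The Conclusion says feasibility and clinical significance are confirmed, but the Statistical Analysis names no feasibility measure and no statistic for the four-grade scan outcome

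*Combined protocol and SAP*

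**What the plan says.** The Conclusion gives the aim: "The purpose of this pilot study was to evaluate the use of a portable ultrasound machine by comparison with an established laboratory-based ultrasound machine". It reports full agreement between the two instruments in stroke risk category, without a denominator, and adds that, as a pilot, "it confirms the feasibility and clinical significance of this investigation". It then asks for a larger sample with a wider range of velocities, and says more evidence is needed on what the differences mean for screening.

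On design, the Methods say "we aimed to study 25 consecutive patients referred to the vascular sciences department for routine TCD scanning". The number rests on patient numbers in the service and a higher-degree timetable ("hence the study duration was limited to six months"). Each child has a full assessment on the laboratory machine, then a repeat on the portable machine limited to the MCA on each side. On outcome, "Each study was categorised as normal, conditional, abnormal or inadequate", by the STOP criteria.

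The Statistical Analysis section lists three methods:

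- Spearman: "Spearman's Correlation Coefficients were calculated to assess the relationships between different parameters in" the study.
- ICC: "Intra-class Coefficient Correlation (ICC) and 95% confidence intervals were used to provide a measure of the strength of the association" between machines, where a value above 0.75 "implies acceptable validity".
- Bland-Altman plots of TAMM velocity, with no acceptable difference stated.

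The four grades do not appear in that section.

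**The concern.** A feasibility claim for a portable scanner rests first on how often it gives a usable reading. The grade inadequate is the recorded item that bears on this most directly, yet no analysis of it is planned and no rule says how such scans are handled. The three velocity methods describe how close two readings are when both exist. They do not show how often both exist.

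The clinical side has a similar gap. Agreement in STOP category is a clinically relevant comparison and is reported, but without a planned statistic, category counts, denominator or interval. With no acceptable velocity difference set, the Bland-Altman plots cannot settle the matter either. A reader could take the Conclusion as support for using the portable machine in screening and would have no figure in this document against which to check it.

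**Working it through.** **1. Claim against plan.**

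| Planned analysis | What it needs | What it answers |
|---|---|---|
| Spearman | A TAMM from both machines | Whether the rankings move together |
| ICC with 95% CI, benchmark above 0.75 | A TAMM from both machines | Validity of the measurement, in the plan's own terms |
| Bland-Altman | A TAMM from both machines | Size of the velocity differences |
| Four-grade outcome | A grade from each machine | No statistic planned |

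None of the rows yields an adequate-scan rate, a completion rate or a success criterion.

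**2. The plan's own figure.** The target of 25 cannot be reproduced, because no power, precision, SD or dropout input is given. It is presented as a convenience number. What can be shown is how much 25 children could support.

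**3. Precision of a proportion at n = 25** (assumptions: all 25 enrolled, one result per child, exact Clopper-Pearson limits).

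- When x = n, the lower limit is 0.025^(1/n). For n = 25 this is 0.025^(1/25) = 0.863, so 25/25 gives 86.3% to 100%. The complement is 1 − 0.863 = 13.7%.
- When x < n, the limits are the 2.5% quantile of Beta(x, n − x + 1) and the 97.5% quantile of Beta(x + 1, n − x).
- 24/25: 79.6% to 99.9%.
- 22/25: 68.8% to 97.5%.
- 20/25: 59.3% to 93.2%.
- If only 20 children could be compared and all agreed, the lower limit would be 0.025^(1/20) = 83.2%.

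The same limits serve for an adequate-scan rate and for category agreement.

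**4. How likely it is that the question arises.** Let p be an assumed rate of scans inadequate on the portable machine only. The documents give none, so a range is shown. The expected loss is 25p, and the chance of at least one is 1 − (1 − p)^25.

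| p | Expected loss out of 25 | Chance of at least one |
|---|---|---|
| 2% | 0.5 | 40% |
| 5% | 1.25 | 72% |
| 10% | 2.5 | 93% |
| 20% | 5 | 99.6% |

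**5. Whether the ICC would reveal it.** The ICC model is not named, so a one-way ICC with two readings and one pair per child is assumed. With F = (1 + r)/(1 − r), an observed r = 0.90 gives F = 1.90/0.10 = 19. The limits are (F_L − 1)/(F_L + 1) and (F_U − 1)/(F_U + 1), where F_L = F divided by the 97.5% point of F(n − 1, n) and F_U = F times the 97.5% point of F(n, n − 1).

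- 25 pairs: 0.79 to 0.95.
- 20 pairs: 0.77 to 0.96.

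At the same observed ICC, losing a fifth of the pairs hardly moves the interval. The velocity analyses would give little sign of a signal-acquisition problem, so it has to be counted separately.

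**The case against.** Four points can fairly be made for the plan.

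- **A clinically relevant comparison was made.** TAMM was chosen because STOP risk categories are based on it, and agreement in those categories is reported. This stands. A reader might infer that nothing at all lies behind the claim of clinical significance, or that clinical outcomes had to be collected. The documents support neither: a method-comparison pilot can rest on risk-category agreement. What is missing is the planned statistic, counts, denominator and interval.
- **Exclusion of inadequate scans is not stated.** A reader might infer that children inadequate on one machine were dropped and that agreement is therefore overstated. The documents do not show this. They neither define inadequate nor describe its handling. A scan graded inadequate on one side, or for a vessel other than the MCA, could still give an MCA pair. If the reported full agreement covers all four grades, no scan was inadequate on one machine only. If it covers gradable scans alone, the question remains. The text does not say which.
- **The claim may be narrow.** It concerns this investigation as a pilot, and can be read as saying that the comparison is practicable and worth repeating at scale. That reading is reasonable, but even so no completion or adequacy measure is named in support, and the verb used is a strong one.
- **The Conclusion limits itself, and there is no results section.** Both are true. Counts may exist elsewhere. The closing caution on screening helps, but it sits uneasily beside a statement that clinical significance is confirmed.

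**Conclusion.** The point holds in a limited form. The Conclusion goes further than the Statistical Analysis section can carry: that section names no feasibility measure and plans no statistic for the four-grade outcome. A vessel with no usable TAMM on one machine contributes to none of the three velocity analyses, so they cannot speak to signal acquisition. This is a gap in analysis and reporting. It is not evidence that the portable scanner performed poorly or that the reported agreement is wrong.

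On size, the most favourable result at the target, 25 of 25 adequate and concordant, has an exact 95% lower limit of 86.3%, so a failure rate of up to 13.7% would not be excluded. This assumes that 25 children were enrolled with one result each. The number analysed, the number inadequate and the category counts are not given.

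**What to change.** 1. For all children actually enrolled (target 25), add a portable-by-laboratory cross-table of the four grades. Grade both machines on the MCA alone, since the portable scan covers no other vessel.
2. From that table report, each with an exact 95% CI, the number inadequate on each machine, the number inadequate on the portable machine only, and category agreement. Say whether agreement includes the inadequate grade.
3. State the number of vessels and of children in each velocity analysis.
4. In the Conclusion, replace the statement that feasibility and clinical significance are confirmed with the observed adequate-scan rate and category agreement, with their intervals, and say that the implications for screening remain open.

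The cost is one extra table, built from grades the Methods say were recorded, and a reworded Conclusion. The downside is a less favourable claim.
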